## 3. Analyses

All analyses will be presented by Arm and for All Patients. Otherwise, specified patient disposition, study drug usage, prior/concomitant/post-ONC201 medications, demographic and baseline characteristics, adverse events, and laboratories will use methods and summaries defined in the ISS SAP.

Laboratory boxplots will be presented for all tests with at least 60 patients having numeric baseline results: one plot per test, time on the x-axis, value on the y-axis. The plots will not be broken out by arm (i.e. only the All Patients group). Only Baseline and Cycles 2-12 will be presented. For Cycles 2-12, nominal visits will be used; if multiple values are associated with a visit, the highest value will be used for chemistry tests and lowest value will be used for hematology tests.

The following efficacy analyses will be performed: best overall response, overall response rate, disease control rate, duration of response, progression-free survival, and overall survival. All analyses will be based on the investigator-assessed overall RANO response. Discontinuation of treatment due to progressive disease will also be considered. All analyses, aside from overall survival, will be censored at

the earlier of: (1) last disease assessment or (2) last assessment prior to initiation of other anticancer therapy.

Cycle 1 (2hr, 24hr, 48hr, 72hr) ONC201 plasma concentrations will be summarized descriptively, including geometric mean and %CV. BLQ results will be imputed as zero.

Collected data contributing to presented tables and figures will be listed.

Other analyses specified in the protocol will either not be completed, or will be defined outside the scope of this plan.

Following is a complete list of the tables, figures, and listings to be prepared (with clarifying notes in parentheses).

Number	Description
Table 1.1	Patient Disposition
Table 1.2	Demographics and Baseline Characteristics
Table 1.3	Study Drug Usage
Table 1.4.1	Prior Medications
Table 1.4.2	Concomitant Medications
Table 1.4.3	Post-ONC201 Medications
Table/Figure 2.1	Progression-free Survival
Table/Figure 2.2	Overall Survival
Table 2.3	Response Rate (includes ORR, BOR, and DCR)
Table/Figure 2.4	Duration of Response
Table 3.x.1*	Treatment-emergent Adverse Events (TEAE)
Table 3.x.2*	TEAE Grade 3 and Above
Table 3.x.3*	Serious TEAE
Table 3.x.4*	TEAE Leading to Death
Table 3.x.5*	TEAE Leading to Study Drug Discontinuation, Reduction, or Interruption
Table 3.x.6*	Study Drug Related TEAE
Table 3.x.7*	Study Drug Related TEAE Grade 3 and Above
Table 3.x.8*	Study Drug Related Serious TEAE
Table 3.x.9*	Study Drug Related TEAE Leading to Death
Table 3.x.10*	Study Drug Related TEAE Leading to Study Drug Discontinuation, Reduction, or Interruption
Table 3.x.11*	TEAE by Maximum Severity (overall only)
Table 3.x.12*	Study Drug Related TEAE by Maximum Severity (overall only)
Table 4.x.1*	Graded Laboratory Results (maximum post-baseline)
Table 4.x.2*	Graded Treatment-emergent Laboratory Results (maximum on-treatment, result only counted if > Baseline Grade)
Table 5.1	Plasma Concentrations
Figure 4.1	Boxplot of Laboratory Results
Listing 1.1	Patient Disposition
Listing 1.2	Demographics and Baseline Characteristics
Listing 1.3	Study Drug Usage
Listing 1.4	Other Medications
Listing 2.1	Efficacy Outcomes
Listing 3.1	Adverse Events
Listing 3.2	AE Leading to Death
Listing 3.3	AE Leading to Study Drug Discontinuation, Reduction, or Interruption
Listing 4.1	Listing of Graded Laboratory Results (includes all results for a patient/test where at least one on-treatment result is $\geq$ Grade 1)
Listing 5.1	Plasma Concentrations

x=1: all post-baseline, x=2: prior to initiation of other anticancer therapy

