Protocol Title: A Phase II, Open-Label Study of ONC201 in Adults with Recurrent High-Grade

Glioma

Protocol Number: ONC013 (NCT03295396) **Protocol Date:** 19 November 2019 (Version 4.0)

PROTOCOL TITLE: A phase II, open-label study of ONC201 in adults with recurrent high-grade glioma

Protocol Version 04

Date: November 19, 2019

Oncoceutics Study Identifier: ONC013

Overall Principal Investigator:
[name]
Department of Neurology & Herbert Irving Comprehensive Cancer Center
Columbia University Irving Medical Center
[name]
[name]

Sponsor:

Oncoceutics, Inc. [name]

Agent(s): ONC201

IND: 136090

Version 01: 10/19/17

Version 02 (Amendment 1): 04/16/18 Version 03 (Amendment 2): 04/23/18 Version 04 (Amendment 3): 11/19/2019

CONFIDENTIAL

The information contained in this protocol is the confidential property of the Sponsor. It is intended solely for the recipient clinical investigator(s) for the purposes of conducting the clinical protocol and may not be reproduced or disclosed to third parties without proper authorization from the Sponsor.

Study Summary

Title	A phase II, open-label study of ONC201 in adults with recurrent high-grade glioma
Short Title	ONC201 in recurrent high-grade glioma
Oncoceutics Protocol Number	ONC013
IND	136090
Overall Principal Investigator	[name] Department of Neurology & Herbert Irving Comprehensive Cancer Center Columbia University Irving Medical Center
Regulatory Sponsor	Oncoceutics, Inc.
Phase	Phase II
Methodology	Open-label, two arm
Study Duration	Approximately 24 months from start of screening to last subject processed and finishing the study
Objectives	 Primary Objective: To estimate the overall response rate (ORR) by RANO-HGG of ONC201 in adults with recurrent histone H3 K27M mutant glioma Secondary Objectives: To estimate the overall response rate (ORR) by RANO-LGG of ONC201 in adults with recurrent histone H3 K27M mutant glioma Assess the safety, toxicities and tolerability of ONC201 in adults with recurrent high-grade glioma (HGG); Estimate the median progression-free survival (PFS), PFS at 2 and 6 months, overall survival (OS), and median duration of response;

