Statistical Methodology	Primary Efficacy Analysis: Simon's two-stage design (Simon, 1989) will be used. The null hypothesis that the true response rate is 0.01 will be tested against a one-sided alternative. Arm A In the first stage, 17 patients will be accrued. If there are 0 responses in these 17 patients, the study will be stopped. Otherwise, 22 additional patients will be accrued for a total of 39. Arm B In the first stage of Arm B, 17 patients will be accrued. If there are 0 responses in these 17 patients, the study will be stopped. Otherwise, 39 additional patients will be accrued for a total of 56. At least 3 responses will be required in order for success to be claimed (i.e. for the null hypothesis ($p_0 \le 0.01$) to be rejected in favor of the alternative ($p_1 \ge 0.10$) with 80% power, alpha=0.025). Patients will be analyzed separately in each arm.

TABLE OF CONTENTS

Stu	dy Summary	2
1.	OBJECTIVES	7
1.1	General Study Design	7
1.2	Primary Objective	8
1.3	Secondary Objectives	8
1.4	Exploratory Objectives	8
1.5	Endpoints	8
2.	BACKGROUND	9
2.1	Study Disease	9
2.2	IND Agent	10
2.3	Clinical Studies	18
2.4	Rationale for ONC201 in Glioblastoma and Histone H3 K27M Gliomas	20
2.5	Correlative Studies Background	24
3.	PARTICIPANT SELECTION	25
3.1	Inclusion Criteria	25
3.2	Exclusion Criteria	27
3.3	Inclusion of Women and Minorities	28
4.	REGISTRATION PROCEDURES	28
5.	TREATMENT PLAN	28
5.1	Treatment Regimen	28
5.2	Screening Procedures	29
5.3	Baseline Procedures	30
5.4	On-Treatment Procedures	31
5.5	Efficacy Procedures	32
5.6	End of Treatment Visit	33
5.7	General Concomitant Medication and Supportive Care Guidelines	34
5.8	Criteria for Taking a Participant Off Protocol Therapy	35
5.9	Duration of Follow Up	35
5.10	O Criteria for Taking a Participant Off Study	36
6.	DOSING DELAYS/DOSE MODIFICATIONS	36
7.	ADVERSE EVENTS: LIST AND REPORTING REQUIREMENTS	37

7.1	Reporting of Serious Adverse Events	38
7.2	Adverse Event Characteristics	39
8.	PHARMACEUTICAL INFORMATION	40
8.1	Drug Substance Description	40
8.2	Drug Product Description	41
8.3	Drug Product Supply, Administration and Inventory	42
9.	BIOMARKER, CORRELATIVE, IMAGING SUBMISSION AND SPECIAL STUDIES	43
9.1	Predictive Tumor Biomarker Studies	43
9.2	Circulating Pharmacodynamic Analyses	43
9.3	Immune Cell Studies	44
9.4	ONC201 Plasma Analyses	44
9.5	Imaging submission	44
10	SCHEDULE OF EVENTS	46
11.	MEASUREMENT OF EFFECT	48
11.1	Response Assessment Criteria	48
11.2	Definitions	48
11. 3	B Disease Parameters	48

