1.2 Primary Objective

• To estimate the overall response rate of ONC201, assessed by RANO-HGG criteria, in adult patients with recurrent histone H3 K27M glioma.

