1.3 Secondary Objectives

- Assess ORR. according to RANO-LGG, criteria for non-contrast enhancing lesions.
- Assess the safety, toxicities and tolerability of ONC201 in adults with recurrent high- grade glioma;
- Estimate the median PFS, PFS at 2 and 6 months, median OS, and median duration of response;

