1.5 Endpoints

-Efficacy

- Response by RANO-HGG
- Response by RANO-LGG
- Duration of response by either RANO-HGG or RANO-LGG
- Progression free survival by RANO-HGG
- Progression-free survival by RANO-LGG
- Overall survival

-Safety

- Adverse events
- Laboratory evaluations
- KPS status
- Vital signs
- Physical examinations

-Other

- Quality of life Assessment by MDASI Patient Reported Outcomes Questionnaire
- NANO (Neurologic Assessment in Neuro-Oncology)

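### SAP section 3 rests every efficacy analysis on one RANO response without naming the criterion, so RANO-LGG response rate and RANO-LGG PFS have no output in its complete list

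*SAP*

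**What the plan says.** Protocol section 1.2 gives the primary objective: "To estimate the overall response rate of ONC201, assessed by RANO-HGG criteria, in adult patients with recurrent histone H3 K27M glioma". The Study Summary lists among the secondary objectives: "To estimate the overall response rate (ORR) by RANO-LGG of ONC201 in adults with recurrent histone H3 K27M mutant glioma". Section 1.3 repeats it in other words: "Assess ORR. according to RANO-LGG, criteria for non-contrast enhancing lesions". Section 1.5 lists response and PFS once under each criterion; the second PFS entry reads "Progression-free survival by RANO-LGG". Duration of response has a single entry: "Duration of response by either RANO-HGG or RANO-LGG". Section 1.1 requires tumor response to be evaluated under both the high-grade and the low-grade criteria.

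SAP section 3 names the efficacy analyses (best overall response, response rate, disease control rate, duration of response, PFS and overall survival) and then says: "All analyses will be based on the investigator-assessed overall RANO response". Neither RANO-HGG nor RANO-LGG appears in the SAP text supplied. The section gives what it calls a complete list of outputs. The efficacy entries are Table/Figure 2.1 (PFS), Table/Figure 2.2 (overall survival), Table 2.3 (response rate, with ORR, BOR and DCR), Table/Figure 2.4 (duration of response) and Listing 2.1 (efficacy outcomes). It adds that other protocol analyses will either be left undone or be defined outside the plan.

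**The concern.** The protocol asks two response questions and two PFS questions, one under each criterion. The SAP provides one response variable, does not name it, and derives one response table and one PFS output from it.

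Two things are at stake. First, a programmer following the SAP would produce no RANO-LGG response rate and no RANO-LGG PFS, so a secondary objective would go unanswered. A reader of the results could not tell whether it had been dropped or reported elsewhere. Second, a reader of Table 2.3 needs to know that the responders are counted by RANO-HGG before treating that rate as the primary result.

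**Working it through.** No arithmetic applies. The check sets the protocol's efficacy endpoints beside the SAP's outputs.

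| Protocol section 1.5 endpoint | Standing in the objectives | SAP output | Criterion named in SAP |
|---|---|---|---|
| Response, RANO-HGG | Primary (1.2) | Table 2.3, if that is the criterion meant | No |
| Response, RANO-LGG | Secondary (Study Summary, 1.3) | None of its own | No |
| Duration of response, either criterion | Secondary (1.3) | Table/Figure 2.4 | No |
| PFS, RANO-HGG | Secondary; 1.3 names PFS without a criterion | Table/Figure 2.1, if that is the criterion meant | No |
| PFS, RANO-LGG | As above | None of its own | No |
| Overall survival | Secondary (1.3) | Table/Figure 2.2 | Not needed |

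**Step 1: what the single response could mean.**
- If it is RANO-HGG, the primary endpoint is covered and RANO-LGG response and PFS have no result.
- If it is RANO-LGG, the primary endpoint has no result. Nothing in the documents suggests this is intended.
- If it merges the two criteria, neither has a result of its own.
- If the word overall only means that imaging and clinical evaluation are combined at a visit, the question of which criterion stays open.

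On each of these readings, at least one response endpoint and one PFS endpoint in the protocol are left without a result.

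**Step 2: whether the list implies one run per criterion.** The SAP marks repeated outputs when it wants them. The adverse event and graded laboratory tables carry an index, with a footnote giving its two values (all post-baseline, and before other anticancer therapy). Outputs 2.1 to 2.4 carry no such index. The parenthetical note on Table 2.3 gives the measures in the table but no criterion.

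**Step 3: whether Listing 2.1 fills the gap.** SAP section 3 says that the data listed are those contributing to the tables and figures presented. If no table uses RANO-LGG, the listing need not contain it. A listing would in any case not be an estimate of a response rate or of PFS.

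**Step 4: whether the general exclusion settles it.** The sentence on other protocol analyses offers two outcomes, not done or defined elsewhere. It says neither which analyses are meant nor which outcome applies to each.

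**The case against.** The strongest reply is that this SAP is openly abbreviated. Section 1 refers to the ISE SAP where approaches are the same, and to the protocol for other details. The ISE SAP was not supplied. The protocol text supplied ends within section 2, so section 11 (measurement of effect) and section 13 (statistics) could not be read. Any of these may define the overall RANO response. That stands as a limit on the unnamed criterion. It carries less weight for the missing outputs, because a definition elsewhere adds no RANO-LGG table to a list declared complete. SAP section 3 also cites the ISS SAP for the non-efficacy summaries but cites no document in its efficacy paragraph.

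A second reply is that the complete list and the general exclusion, read together, disclose that anything unlisted is dropped or deferred. This stands in part: the SAP does not promise a RANO-LGG analysis and then fail to deliver it. What it leaves open is which of the two outcomes applies to a stated secondary objective.

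A third reply is that RANO-LGG PFS is only an entry in the endpoint list, since section 1.3 names PFS without a criterion. That is correct, and it makes the PFS part weaker than the response part.

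A reader might go further and infer that the primary decision cannot be made because no output states the two-stage result. The documents do not support that. The protocol says "Patients will be analyzed separately in each arm", and SAP section 3 presents all analyses by arm, so the count in Table 2.3 can be set against the protocol's rule by hand once its criterion is known. Adding a cutoff row would not be safe on the present text. The sentence "At least 3 responses will be required in order for success to be claimed" appears once, after the description of Arm B, and does not say whether it covers Arm A. The protocol also sizes the arms in evaluable subjects, while the SAP analyzes all treated patients.

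**Conclusion.** The concern holds as a gap in coverage and labelling. On the supplied text, one secondary objective (response rate by RANO-LGG) and one listed endpoint (PFS by RANO-LGG) have no output, and the criterion behind the primary response rate is not named. The size cannot be put as a change in a rate, because the documents do not say how often the two criteria would classify a patient differently.

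Three stronger inferences are not supported:
- That the sponsor has replaced RANO-HGG as the primary criterion. The SAP is silent; it does not state a different criterion.
- That type I error or power is affected. Nothing here alters the protocol's decision rule.
- That the single duration of response output departs from the protocol. Section 1.5 lists that endpoint once, under either criterion, so only a label is missing.

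The conclusion assumes that the list is complete, as the SAP says, and that no unseen document already assigns the RANO-LGG analyses. Confidence is moderate for that reason.

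**What to change.** In SAP section 3, state that the primary response rate is by RANO-HGG. Produce Table 2.3 and Table/Figure 2.1 separately by RANO-HGG and by RANO-LGG, with the criterion in each title. Label the criterion used in Table/Figure 2.4 as well. If RANO-LGG has been moved to another document, name that document in section 3.

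The cost is a few sentences and a few extra tables. Protocol section 1.1 already requires evaluation by both criteria, so no new assessments should be needed. This assumes that the investigator's two calls are recorded separately, which the supplied text does not confirm and the sponsor should check first.

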1.1 General Study Design

This is an open-label, two arm study. The trial will enroll a total of up to 95 subjects. Arm A will enroll up to a total of 39 evaluable subjects and Arm B will enroll up to a total of 56 evaluable subjects. A Bayesian monitoring approach will be applied to assess safety throughout the trial.

After screening procedures and registration, all subjects will be treated with oral ONC201 (625 mg) once every week. All subjects will remain on study until confirmed progressive disease, unacceptable toxicity, death, withdrawal of consent, or another protocol criterion for subject withdrawal is met, whichever comes first. One treatment cycle will be defined as 28 days (4 weeks), corresponding to 4 doses of ONC201.

Subjects will be evaluated for efficacy approximately every 8 weeks with neuroimaging and clinical evaluation. Neuroimaging studies contrast-enhanced brain MRI or CT for patients unable to undergo MRI) will be performed at baseline and every 8 weeks after treatment initiation. Tumor response will be evaluated by the Response Assessment in Neuro-Oncology (RANO) criteria, both criteria for HGG and low-grade glioma (LGG).

Subjects will be evaluated for safety if they have received any study drug. Toxicity assessments will be continuous during the treatment phase. Adverse events will be monitored throughout the trial and graded in severity according to the guidelines outlined in the NCI Common Terminology Criteria for Adverse Events (CTCAE) version 5.

End of treatment assessments will be performed within 30 days after last drug administration, unless the subject is unable to travel due to deteriorating medical condition. Post-treatment, all participants will be followed until resolution or stabilization of any serious or reportable adverse events occurring during treatment or starting within 30 days of last study drug. Assessments may continue for ongoing reportable adverse events.

Subjects who discontinue study drug must continue to be followed for collection of outcome and/or survival follow-up data until death, withdrawal of permission to record at least survival data, or subject is lost to follow-up. Following the end of treatment assessments, all subjects will be contacted every 30 days (±7 days) to assess for study-treatment related toxicities, initiation of any new anti-cancer treatments, and survival status. Contact may be performed by a site visit, telephone contact, e-mail, fax, or mail.

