## 1. Introduction

This abbreviated Statistical Analysis Plan (SAP) describes the statistical analyses to be conducted for the Study ONC013. For simplicity, reference is made to existing Integrated Summary of Safety (ISS) and Integrated Summary of Efficacy (ISE) SAPs when approaches are the same.

Study ONC013 is a Phase II, open-label, multi-center clinical trial of ONC201 in adult recurrent glioma with two arms. All subjects receive oral ONC201 at 625 mg every week. All subjects remain on study until progressive disease, unacceptable toxicity or withdrawal of consent. For other study details, refer to the study protocol.

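### Does the SAP's censoring sentence remove deaths between scans from progression-free survival and duration of response?

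*SAP*

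**What the plan says.** SAP section 3 lists best overall response, response rate, disease control rate, DOR, PFS and overall survival, and bases them on the investigator's overall RANO response. It adds one further source of events: "Discontinuation of treatment due to progressive disease will also be considered". The censoring rule comes next. It exempts only overall survival, and for everything else the date is "the earlier of: (1) last disease assessment or (2) last assessment prior to initiation of other anticancer therapy".

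For disposition, baseline and safety summaries, section 3 points elsewhere: "laboratories will use methods and summaries defined in the ISS SAP". It gives no such pointer for efficacy. The SAP's Introduction does: it describes the plan as abbreviated and says that "reference is made to existing Integrated Summary of Safety (ISS) and Integrated Summary of Efficacy (ISE) SAPs when approaches are the same".

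In protocol section 1.1, imaging is "performed at baseline and every 8 weeks after treatment initiation". Patients are contacted every 30 days after treatment about "initiation of any new anti-cancer treatments, and survival status". Protocol section 1.3 makes median PFS, PFS at 2 and 6 months, and median DOR secondary objectives.

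**The concern.** The sentence lacks two things usually found beside a censoring rule: a list of events, and a statement that the date is for patients who have none. A death without documented progression always falls after the last disease assessment. If that assessment date is a hard cutoff, every such death becomes a censored observation, and a patient who dies before the first post-baseline scan is censored at baseline.

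Scans are 8 weeks apart in recurrent high-grade glioma, so some deaths between scans are plausible. The protocol also excuses patients from the end-of-treatment visit in some cases ("unless the subject is unable to travel due to deteriorating medical condition"). Dropping these deaths would push PFS upward, and all patients receive ONC201, so no untreated control would share the bias. Two programmers could, in principle, produce different curves from the same text.

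**Working it through.** **1. Which reading fits the paragraph?** The plan gives no PFS or DOR figure to reproduce, so the first check is on the wording.

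- *Every patient is censored at the stated date.* Progressions would vanish too, and the planned PFS table and figure would have no events. The sentence would also censor response and disease control rates, which has no meaning. This cannot be intended.
- *The date is a cutoff.* Progression seen at the last scan counts and anything later does not. Stopping treatment for progression normally follows the last scan, so the sentence that counts such discontinuations would then do almost nothing unless they were back-dated, which the SAP does not say.
- *The date is where event-free patients are censored.* Every sentence then has a purpose. The exemption of overall survival also makes sense, because survival is followed by contact and not by scan.

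Only the third reading is ordinary practice and consistent with its neighbours. Under it, death counts by the ordinary meaning of PFS.

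**2. Is the definition really absent?** This cannot be shown. The protocol's contents list section 11.4 (response and progression categories) and section 13.3 (statistical methods for efficacy and safety), but the text available ends within section 2.2.4.2. The ISE SAP was not available either. Since the ISE concerns efficacy, the Introduction's reference to its SAP can hardly bear on anything else.

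**3. What would the cutoff reading cost?** All inputs here are assumed except the 56-day scan interval. Time to first event is exponential with median *M* months (30.4375 days each). A share *d* of first events are deaths dated exactly; the rest are progressions dated at the next scan. Let λ = ln 2 / (30.4375 *M*) and *q* = 1 − exp(−56λ). Six months is 182.625 days: three scans (day 168) plus 14.625 days.

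- Deaths as events: PFS6 = (1 − *q*)³ × [1 − *d*(1 − exp(−14.625λ))].
- Deaths censored at the previous scan: in each interval *dq* leave the risk set, and (1 − *d*)*q* of the remaining 1 − *dq* progress. The survival factor is (1 − *q*)/(1 − *dq*), so PFS6 = [(1 − *q*)/(1 − *dq*)]³.

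Example with *M* = 2.5 and *d* = 0.10: λ = 0.00911 and *q* = 0.3996. Deaths as events: 0.6004³ × (1 − 0.1 × 0.1247) = 0.2165 × 0.9875 = 0.214. Deaths censored: (0.6004/0.9600)³ = 0.6254³ = 0.245. The difference is 3.1 points.

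| Assumed median (months) | PFS6, *d* = 10%: event v censored | PFS6, *d* = 30%: event v censored | Estimated median day, *d* = 30% |
|---|---|---|---|
| 2 | 14.5 v 17.1% (+2.5) | 14.1 v 23.3% (+9.2) | 74 v 112 |
| 2.5 | 21.4 v 24.5% (+3.1) | 20.8 v 31.8% (+10.9) | 112 v 112 |
| 4 | 38.1 v 41.8% (+3.6) | 37.5 v 49.7% (+12.1) | 147 v 168 |
| 6 | 52.6 v 56.0% (+3.4) | 52.0 v 63.1% (+11.1) | 221 v 280 |

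Differences are taken before rounding. The medians use the same formulas after *k* scans. For *M* = 2 and *d* = 0.30, λ = 0.01139 and *q* = 0.4715. With deaths as events the curve is 0.5285 × [1 − 0.3(1 − exp(−λ*u*))] at *u* days after day 56; it reaches 0.5 at *u* ≈ 17.4, about day 74. With deaths censored it is 0.5285/(1 − 0.1415) = 0.616 at day 56 and 0.616² = 0.379 at day 112, so the median is day 112. The bias would therefore not be confined to the landmark rates.

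A 10% share is about 4 of 39 patients in Arm A and 6 of 56 in Arm B. A patient who worsens between scans, stops for progression and then dies can already be an event through the discontinuation clause, which lowers *d*. The calculation has no such route. DOR was not quantified.

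**The case for a change.** The best argument for a change is that the authors chose what to write. They considered events beyond the RANO reading and added discontinuation for progression but not death. They considered exceptions and exempted only overall survival. The efficacy rule has no reference of its own, and if another document defines PFS conventionally, this sentence still sits awkwardly beside it. The cure would be a few words, using dates the trial already collects.

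Some of this stands: the wording is loose, and a reader with only this text has to supply the event definition. The inference from the omission is weak, though. Discontinuation for progression is not automatically a PFS event when the analysis rests on RANO assessments, so it needs saying; death is part of the endpoint's name. Overall survival needs its exemption under the conventional reading too, because its follow-up does not end with the last scan. The end-of-treatment exception concerns a visit after the last dose, and such patients may already have stopped for progression, so it does not show that deaths before progression are common.

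**Conclusion.** No change to the plan is needed. The sentence leaves out a detail that analysts fill in the same way as a matter of routine: patients with progression or death have events, and the rest are censored at the stated assessment. The harmful result needs an unconventional reading that fits poorly with the discontinuation clause beside it. That the definition is missing cannot be established without protocol sections 11.4 and 13.3 and the ISE SAP.

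The effect is zero if deaths count. If they were censored, 6-month PFS would be about 2.5 to 12 points too high for assumed death shares of 10% to 30% and assumed medians of 2 to 6 months, and the estimated median could move by up to about two months (221 to 280 days, or 59 days, in the largest case shown). The documents support none of those shares or medians. PFS and DOR are secondary estimates with no test or threshold attached in the text available, and the primary rule, which counts responses, does not depend on this sentence's treatment of deaths. How to date a discontinuation for progression, and whether to add a sensitivity analysis for deaths after new therapy, are matters of preference.

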## 2. General Conventions

The All Treated Analysis Set includes all patients who receive at least one dose of ONC201. This will be used for all analyses.

Unless otherwise specified, continuous variables will be summarized using descriptive statistics [number of observations, mean, standard deviation (SD), median, 1st (Q1) and 3rd (Q3) quartiles, minimum and maximum]. Categorical variables will be summarized as number (percent) of patients.

Day 1 is defined as the date of the first dose of study drug. For events that occur on or after Day 1, study day is defined as (date of event - date of Day 1 + 1). For events that occur prior to Day 1, study day is defined as (date of event - date of Day 1). There is no Day 0. Baseline is defined as the last observed measurement on or before the date of the first dose of study drug.

In general, other than for partial dates, missing data will not be imputed and will be treated as missing. Unless otherwise specified, partial dates will be imputed using the following rules:

- If year is missing, do not impute.
- If only day is missing, impute day as 1st of the month for start dates, end of the month for end dates, and 15th of the month for other dates.
- If day and month are missing, impute as January 1st for start dates, December 31st for end dates, and July 1st for other dates.

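### Setting BLQ plasma concentrations to zero makes the geometric mean in SAP Table 5.1 zero or not computable wherever a BLQ value occurs

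*SAP*

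**What the plan says.** SAP section 3 defines the plasma summary in one sentence: "Cycle 1 (2hr, 24hr, 48hr, 72hr) ONC201 plasma concentrations will be summarized descriptively, including geometric mean and %CV". The sentence after it is the whole BLQ rule: "BLQ results will be imputed as zero". The rule carries no condition and no exception.

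Three other statements set the scope:

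- The same section says "All analyses will be presented by Arm and for All Patients", so each time point has one cell per arm and one pooled cell.
- SAP section 2 says that, by default, "continuous variables will be summarized using descriptive statistics". Those are n, mean, SD, median, quartiles, minimum and maximum. The geometric mean and %CV are additions made for this table.
- The analysis population is wide: "The All Treated Analysis Set includes all patients who receive at least one dose of ONC201", and this set serves all analyses.

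Nothing in the text reviewed qualifies the BLQ rule. SAP section 3 hands several topics to another document, ending with "adverse events, and laboratories will use methods and summaries defined in the ISS SAP", but plasma concentrations are not among them. Some entries in the list of outputs carry a clarifying note; Table 5.1 does not.

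**The concern.** A geometric mean uses the logarithm of every value, or equivalently the product of all of them, so it needs every value to be positive. The SAP names this statistic and in the next sentence prescribes a value on which it cannot work. The rule takes effect only when a BLQ result occurs, and in exactly that case it breaks the statistic.

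At stake is the content of Table 5.1. A zero or a blank would at least be visible. The less visible outcome is that software or a programmer drops the zeros and prints a positive geometric mean. That would depart from the stated rule, bias the value upward and rest on a smaller n than the rest of the row.

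**Working it through.** **Inputs.** The BLQ rule, the named statistics and the by-arm layout come from SAP section 3. Planned numbers are 39 (Arm A), 56 (Arm B) and 95 in total (Protocol Study Summary and section 1.1). An arm that stops at its first stage has 17: "If there are 0 responses in these 17 patients, the study will be stopped". Protocol section 2.2.4.2 gives, for 625 mg, a mean half-life of 11.3 h and a Cmax of 3.6 µg/mL at 1.8 h. The documents reviewed give no LLOQ, BLQ rate or number of patients sampled. The plan states no figure of its own on this point, so there is none to reproduce.

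**Step 1: one zero in the formulas.**

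- Product form: (x1 × … × xn)^(1/n) = 0 if any x is 0.
- Log form: exp(mean of ln x). Since ln 0 is minus infinity, software returns 0, an error or a missing value.
- Geometric %CV: √(exp(var(ln x)) − 1), which is not computable.

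In a simulated cell of 39 values with the smallest set to 0, the geometric mean came out as 0 by both forms and the geometric %CV as not-a-number. The arithmetic mean and arithmetic %CV remained computable.

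**Step 2: contrast with the arithmetic mean.** With one zero among n values, the mean is (n − 1)/n times the mean of the other values. It is therefore lower by 1/n: 5.9% at n = 17, 2.6% at 39, 1.8% at 56 and 1.1% at 95. The effect on the geometric mean does not shrink with n.

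**Step 3: the answer depends on the rule.** Take assumed values 40, 50, 60 and one BLQ.

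| Rule | Geometric mean |
|---|---|
| Zero, as written | 0 or not computable |
| BLQ value dropped | (40 × 50 × 60)^(1/3) = 49.3, on n = 3 |
| LLOQ/2, LLOQ assumed 0.5 | (40 × 50 × 60 × 0.25)^(1/4) = 13.2 |
| LLOQ/2, LLOQ assumed 1 | 15.7 |
| LLOQ/2, LLOQ assumed 5 | 23.4 |

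**Step 4: where BLQ values are likely.** Assuming mono-exponential decay from the protocol's mean values, C(t) = 3600 × 0.5^((t − 1.8)/11.3) ng/mL. This gives about 3,556, 922, 212 and 49 ng/mL at 2, 24, 48 and 72 h. The typical 72 h value is about 1.4% of Cmax (49/3,600). With an assumed LLOQ of 1, 5 or 10 ng/mL, a patient with that Cmax would be BLQ at 72 h if the half-life were below about 5.9, 7.4 or 8.3 h, from 70.2 × ln 2 / ln(3600/LLOQ). At 48 h the limits are about 3.9, 4.9 and 5.4 h.

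**Step 5: chance of at least one BLQ value (illustration only).** If a fraction p of samples at a time point is BLQ, independently, and all n patients are sampled, the chance is 1 − (1 − p)^n.

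| n | p = 1% | p = 2% | p = 5% |
|---|---|---|---|
| 17 | 16% | 29% | 58% |
| 39 | 32% | 55% | 86% |
| 56 | 43% | 68% | 94% |
| 95 | 62% | 85% | 99% |

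**Step 6: effect of LLOQ/2.** With one BLQ value at LLOQ/2 and the others' geometric mean at R × LLOQ, the overall geometric mean is (1/(2R))^(1/n) times that of the others. For assumed R from 2 to 50 it is lower by 8% to 24% at n = 17, 3% to 11% at 39, 2% to 8% at 56 and 1% to 5% at 95.

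**The case against.** The strongest reply concerns importance. The problem is conditional, and the protocol's pharmacokinetic figures suggest it is largely confined to 72 h; the 2 h and 24 h cells are probably unaffected, apart from missed or unabsorbed doses. The probabilities in step 5 rest on assumed BLQ rates and full sampling, which the documents reviewed do not establish. The default statistics survive, and the raw values will be available because "Collected data contributing to presented tables and figures will be listed". A zero or blank would be noticed. LLOQ/2 is only one possible remedy: leaving BLQ values out of the geometric mean with their number shown, or printing that it was not calculated, would also remove the conflict. If %CV is arithmetic, nothing fails there.

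Most of this stands, and it limits the size of the point. It does not remove the conflict. The SAP expects BLQ results, since it has a rule for them, and that rule fails in the case it was written for. The existence of several workable remedies with different answers (step 3) is a reason to choose one in advance. The %CV issue is an ambiguity to settle, not a second error.

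**Conclusion.** The concern holds, as a minor point. In any cell with at least one BLQ result, the rule as written gives a geometric mean of 0 or none at all. This follows from the definition and needs no assumption. The same applies to %CV if the geometric form is intended.

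How often it will happen cannot be derived without the LLOQ, the spread between patients and the number sampled; Protocol section 9.4, on plasma analyses, was not in the text available for this review. The location at 72 h rests on mean values and simple exponential decay. The n values are planned evaluable or first-stage numbers, whereas the analysis set is all treated patients, so actual n may differ.

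The effect is confined to one descriptive table. No objective or endpoint in Protocol sections 1.2 to 1.5 uses plasma concentration.

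**What to change.** Replace the BLQ sentence in SAP section 3 with a two-part rule:

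- Zero for the default statistics of SAP section 2 and for any arithmetic %CV.
- LLOQ/2 for the geometric mean and any geometric %CV.

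State which %CV is meant, and add n (%) BLQ at each time point to Table 5.1.

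The cost is one SAP sentence, one table row and a footnote saying that the arithmetic and geometric statistics treat BLQ values differently. The drawback is that LLOQ/2 is a convention: if many samples at a time point are BLQ, the geometric mean depends heavily on the LLOQ. The n (%) BLQ row would show this. If the sponsor prefers another explicit rule, the essential requirement is that it be stated in advance along with the BLQ count.
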